5.13 Example Meal Choices

The following meal choices are examples that may be used during clinic visits 3-8.

Meal Choice 1	Description	Portion Size	Carbohydrate (g) per portion	Sugar (g) per portion	Protein (g) per portion	Fat (g) per portion	Fiber (g) per portion
6" sub roll or flat bread Acceptable substitute: 2 large slices of whole grain sandwich bread	Ex: Subway wheat roll or multigrain flatbread	71g	40	5	7	2	5
4 oz. ham, turkey, chicken, beef (this would be "double	Subway or similar deli cuts	112g	4	1	28	2-8g depending upon choice	0

Meal Choice 1	Description	Portion Size	Carbohydrate (g) per portion	Sugar (g) per portion	Protein (g) per portion	Fat (g) per portion	Fiber (g) per portion
meat" for subway 6" sub)							
1 oz. cheese	Ex: Swiss, monteray jack, provolone, American, cheddar	28g	0	0	6	10	0
Lettuce, 2-3 slices tomato Additional vegetables or small salad acceptable	-	41	2	0	0	0	1
1 Tbsp mayonnaise, 2 T lite mayo or 1 Tbsp oil	Varies	15	0	0	0	12	0
1 1/2 oz. chips – whole grain if possible	Ex: Sunchips at Subway	43	29	3	4	9	3
1 ½ oz cookie - OR-	Ex: Choc Chip at Subway	45	30	18	2	10	1
Medium piece of fresh fruit or equivalent	Ex: 2 packages of Subway apple slices, 8" banana	Varies	30	26	0	0	4
Water or other zero calorie beverage	Ex: water, diet coke	8-16 oz.	0	0	0	0	0
			105	27-35	45-47	35-51	10-13

Meal Choice 2	Description	Portion Size	Carbohydrate (g) per portion	Sugar (g) per portion	Protein (g) per portion	Fat (g) per portion	Fiber (g) per portion
6 oz. Grilled Chicken	Ex: Applebee's "Create Your Masterpiece Menu" Grilled Chicken Breast	168g or 6 oz.	2	0	42	4	0
9 oz baked potato – seasoned 2 tsp butter or margarine	Ex: Applebees "Choice of Sides" Baked Potato	252g or 9 oz.	41	0	6	24	3
Steamed broccoli – seasoned lightly with butter, margarine or oil	Ex: Applebees "Choice of Sides" Steamed Broccoli	84g	2	0	2	8	3

Meal Choice 2	Description	Portion Size	Carbohydrate (g) per portion	Sugar (g) per portion	Protein (g) per portion	Fat (g) per portion	Fiber (g) per portion
Dinner Roll – 2 oz.	Ex: Applebee's kid's sized burger roll	56g	30	4	5	1	0
1 tsp butter or margarine (for roll) – optional	-	1tsp	0	0	0	9	0
Medium piece of fresh fruit or equivalent	1 8" banana 2 c. melon	Varies	30	26	0	0	4
			105	30	55	38-46	10

Low Glycemic Breakfast*	Description	Portion Size	Carbohydrate (g) per portion	Sugar (g) per portion	Protein (g) per portion	Fat (g) per portion	Fiber (g) per portion
2 slices whole grain toast	Preferably Whole grain	28g	30	4	5	-	4
1 tsp butter or margarine	-	1 tsp	0	0	0	9	0
2 Scrambled Eggs or 3 Egg Whites – prepared with up to 1 tsp. fat Optional: Cheese/veggies mixed into eggs	-	2 eggs ¼ c.	0 1	0 0	14 2-7	5-8 0-5	0 0
Coffee – if desired	Limit to 10 oz. for caffeine	10 oz.	0	0	0	0	0
Non-calorie sweetener	-	User preference	-	-	-	-	-
Up to 2 Tbsp milk or cream	Milk can be whole, 1%, 2% or skim	2T	Negl.	0	Negl.	0-4g	0
			30-31	4	21-28	14-34	4

*Overall Guidelines: Limit Carbohydrate to 30g. No fruit juice, no milk beyond any used in coffee. Fruit acceptable up to 15g portion.

5.14 Discharge instructions – Sensor accuracy visits

The discharge procedure will occur upon completion of visit related activities. Blood glucose (either SMBG or YSI) and ketone measurements will be assessed. If the glucose level is <75 mg/dL or ≥300 mg/dL, corrective action will be taken by the investigator as below:

- If plasma glucose is <75 mg/dL, carbohydrates or other medically necessary and appropriate interventions will be administered to raise the glucose to ≥ 75 mg/dL.
- If plasma glucose is >300 mg/dL, fingerstick ketones will be checked and the Inpatient Hyperglycemia and Ketone Treatment guidelines will be followed.

The subject will be discharged once plasma glucose is:

- 100-300 mg/dL and stable or rising in this range for 2 consecutive glucose measurements at least 15 minutes apart, and ketone is ≤ 0.6 mmol/L; or
- >75 -100 mg/dL and rising for 2 consecutive glucose measurements at least 15 minutes apart, and ketone is ≤ 0.6 mmol/L.
- Subjects should not be released if BG is <100 mg/dL and not rising.
- Site will document any adverse events that may have occurred during the visit.

**These measurements should be taken after approximately 60-90 minutes since the last administration of fast-acting bolus insulin.*

Additional inpatient time for BG stabilization will not be considered an adverse event or protocol deviation.

Subjects will be provided a standard meal or snack as necessary during the last hour of visit prior to release to prevent post-discharge hypoglycemia. Snacks will be available in the clinic for subjects to take with them on the ride home.

A clinician trained in the treatment of diabetes should also discuss and make recommendations about each subject's insulin regimen for the remainder of the day to prevent post-visit rebound hypoglycemia which can occur 12 hours later.

5.15 Photograph/Videography

The procedure for inserting or removing the sensors may be photographed and/or recorded on video after receiving subject authorization in writing. Only the area immediately nearby the sites will be photographed and/or recorded and subjects will not be identifiable.

6 CLINICAL LABORATORY EVALUATIONS AND ESTIMATED BLOOD VOLUMES

Standard clinical laboratory analysis equipment, procedures and quality control will be used for all laboratory evaluations in this clinical trial. Blood samples will be drawn at Visits 1 through 8 (or sensor removal as appropriate) for laboratory dexamethasone measurement. Additionally designated subjects across the study will have blood samples drawn for dexamethasone

measurement 3 times on the insertion date, and on each day between visits 3 and 4. Samples for hemoglobin A1C measurement will also be collected at Visit 1, 6, 7 and 8. Hematocrit will be assessed using local lab or Point of Care testing device.

Total Estimated Blood Loss

Maximum estimated blood loss over the study is 504 mL.

7 SUBJECT SAFETY, STOPPING RULES, AND STUDY EXIT

7.1 Diabetes and Safety Considerations during Clinic Visits

Diabetes care in the Clinic Visit will be the responsibility of the Investigator and appropriately delegated staff. As diabetes self-management is an integral part of diabetes care, the Investigator may work closely with the Study subject, when appropriate, to determine the best approach, however the ultimate responsibility lies with the Investigator.

7.1.1 Medical oversight

There will be staff trained in emergency response, and there will be an EKG and emergency cart available at the site at all times. Site-specific safety guidelines will be utilized for subject safety management during periods of hyperglycemia (including monitoring blood ketones) and hypoglycemia. Study staff (MD, DO, or NP who has experience in diabetes management) will also be immediately available at all times during hypoglycemia and hyperglycemia challenges. A nurse, nurse practitioner, or physician will be at the bedside or on the unit throughout the entire visit.

7.1.2 Sensor Site

The sensor insertion sites will be assessed (visually, as well as by palpation, and by eliciting Subject history) at each clinic visit, and the Subject will be instructed to call the clinic if signs or symptoms of irritation or infection (increased temperature, pain, redness, warmth, swelling, or purulence) are observed at any time. Sensor site infections are to be treated with antibiotics, either topical or oral.

At any time during the study if the study physician determines that there is an infection at the sensor insertion site that has not responded to treatment within 3 days, study procedures other than safety procedures will be stopped, and the sensor will be removed. In the event of an insertion site infection and sensor removal, the subject will be withdrawn from the study and not replaced.

7.1.4 Hypoglycemia

The Subject will be asked to alert the study team anytime he or she experiences symptoms of hypoglycemia (i.e., shakiness, dizziness, sweating, headache, moodiness, difficulty concentrating, or the Subject’s usual symptoms of hypoglycemia). The symptoms will be confirmed by Subject SMBG Meter and/or YSI.

Intravenous access is to be maintained during the Clinic Visit and available for hypoglycemia treatment as indicated. Glucagon by injection and IV dextrose will be available at the site and may be used as clinically indicated. A heating pad or heating chamber may be used during the session to minimize potential for occlusion or to enable the insertion of the port.

YSI and/or Subject SMBG meter BG will be checked every 5 minutes until glucose >75 mg/dl.

7.1.4.1 Guidelines for treatment for hypoglycemia

During hypoglycemia challenge or monitoring period, site will follow section 5.12 hypoglycemia challenge table. Subject safety prevails and Investigator may treat for hypoglycemia when clinically indicated.

Subjects will be treated for hypoglycemia as appropriate according to the following table:

Glucose level	Glucose administration	Safety
<60 mg/dL	Treat hypoglycemia as appropriate using oral carbohydrates such as glucose tablets or juice (~15 g. and check glucose in 15 minutes minimum, repeat) until BG >60 mg/dL	If subject is unable to ingest glucose orally, IV dextrose (~2-3 mL/kg D10 intravenous or up to 30 ml D50%) may be used. Glucagon will be available for emergency.
60 – 75 mg/dL	Treat hypoglycemia as appropriate using oral carbohydrates such as glucose tablets or juice (~10 g. and check glucose in 15 minutes minimum, repeat) until BG >60 mg/dL	

- Glucose <60 mg/dL will be treated orally with fast acting carbohydrate as tolerated by the subject and as needed until a glucose level of ≥ 75 mg/dL is achieved.
- Risk for severe hypoglycemia is defined as any of the following situations:
 - Glucose <50 mg/dL
 - The subject is unable to cooperate with oral treatment of hypoglycemia
 - The glucose is dropping at a rate that may not respond adequately to oral treatment
 - The subject experiences symptoms of neuroglycopenia (e.g. lethargy, disorientation, confusion [disordered processing of information or communication], or inappropriate behavior)
 - The subject experiences symptoms of severe hypoglycemia (i.e. hypoglycemic seizure or loss of consciousness)

- In the event that there is NO intravenous access and the subject is at risk for severe hypoglycemia (as defined above), the subject will be treated with 1 mg of glucagon subcutaneously or intramuscularly.
 - The drug will be reconstituted and administered per package insert/instructions.
 - Glucagon may be repeated as needed every 20 minutes to achieve glucose level ≥ 75 mg/dL. Once the subject is able to consume oral treatment, the subject will be treated orally with fast acting carbohydrate as needed until a glucose level of ≥ 75 mg/dL is achieved. Orange juice and milk will be avoided after glucagon administration.
 - Attempts will be made to reestablish intravenous access.
- The accuracy (sampling) visit will be stopped if the subject experiences a hypoglycemic seizure or loss of consciousness and only safety procedures will be continued. The study physician or nurse practitioner will take control over glucose sampling decisions in order to stabilize the subject's glucose between 100-300 mg/dL and determine the appropriate subject disposition (i.e. home or medical facility).

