5.12.3.2 Hypoglycemia challenge guidelines

Glucose level	Insulin administration (challenge initiation)	Glucose administration	Duration* (Approx.)	Safety
<60 mg/dL	None	After 30 minutes and targeted points achieved, treat	30 minutes	If subject is unable to ingest glucose orally, IV

Glucose level	Insulin administration (challenge initiation)	Glucose administration	Duration* (Approx.)	Safety
		hypoglycemia using glucose tablets (15 g. and check in 15 minutes, repeat) until BG >60 mg/dL		dextrose may be used. Glucagon will be available for emergency.
60 – 75 mg/dL	None	None	120 minutes (including 30 minutes below 60 mg/dL)	
> 75 but <180 mg/dL	SQ fast-acting insulin to be delivered targeting 60 mg/dL based on subject's insulin sensitivity ratio. Bolus insulin may not be delivered or repeated unless 3 hours after previous dose.	None		

*Once Hypoglycemia challenge durations have been met (120 minutes <75 mg/dL including 30 minutes <60 mg/dL), the challenge should be ended by inducing a controlled raising of the subject's BG to the normal range (75-120 mg/dL) using glucose tablets or food. Once the subjects BG is normal, glucose control will be free range.

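### In the Protocol 7.1.4.1 table, the 60-75 mg/dL row stops repeat carbohydrate at >60 mg/dL, the bottom of its own range, while the related end points go to at least 75

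*Protocol*

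**What the plan says.** Protocol 7.1.4.1 opens by sending sites to the 5.12 challenge table during a hypoglycemia challenge or monitoring period. It then gives its own treatment table by glucose level.

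- **60-75 mg/dL row.** A first dose is directed: "Treat hypoglycemia as appropriate using oral carbohydrates such as glucose tablets or juice (~10 g". The full dose and repeat rule is "10 g. and check glucose in 15 minutes minimum, repeat) until BG >60 mg/dL".
- **<60 mg/dL row.** The dose is larger and the stop is the same: "15 g. and check glucose in 15 minutes minimum, repeat) until BG >60 mg/dL".
- **First bullet below the table.** Glucose below 60 is treated orally "as tolerated by the subject and as needed until a glucose level of ≥ 75 mg/dL is achieved".
- **Glucagon bullet.** "Glucagon may be repeated as needed every 20 minutes to achieve glucose level ≥ 75 mg/dL". Oral treatment after glucagon has the same ≥75 target.

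Other places in the Protocol:

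- **7.1.4** has glucose checked every 5 minutes until it exceeds 75 mg/dL.
- **5.14** says that for glucose below 75 before discharge, "interventions will be administered to raise the glucose to ≥ 75 mg/dL".
- **5.12.3.2, <60 row** repeats carbohydrate with the same lower stop: "15 g. and check in 15 minutes, repeat) until BG >60 mg/dL". Its 60-75 row gives no glucose. Its footnote ends the challenge by a controlled raising of the subject's "BG to the normal range (75-120 mg/dL) using glucose tablets or food".

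**The concern.** A repeat rule should stop when the subject has left the range being treated. The rule in the 60-75 row is already satisfied at every value above 60, before any carbohydrate is given. After the first dose of about 10 g, a check reading of, say, 65 mg/dL meets the printed stop, so the rule has almost no effect.

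The ≥75 oral bullet does not repair this for everyone, because it covers only glucose below 60. The oral follow-on to ≥75 applies only after glucagon. For a subject first seen at 61-74 and treated outside the 5.12 table, the 60-75 row is the only place in 7.1.4.1 that gives an oral dose and a repeat rule by glucose level.

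What is at stake is a subject-safety instruction in a study that gives insulin to induce low glucose. Staff could take the table as supporting one dose and no more while glucose is still below 75.

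**Working it through.** There is no calculated figure in the plan to reproduce. The check compares the row's entry range with its stop, and then with the end points set elsewhere.

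**1. Entry range against stop (7.1.4.1 table, whole-number readings).**

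- Values in the row: 60 to 75, so 75 − 60 + 1 = 16.
- Values meeting >60: 61 to 75, so 15.
- Values meeting ≥75: 75 only, so 1.
- Values where the two stops give different instructions: 15 − 1 = 14 (61 to 74), and 14/16 = 87.5%.
- At 60 both stops call for a repeat; at 75 neither does.
- Gap between the stops: 75 − 60 = 15 mg/dL.

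**2. Low-glucose end points side by side.**

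| Place in Protocol | Applies to | End point (mg/dL) |
|---|---|---|
| 7.1.4.1 table, 60-75 row | 60-75 | >60 |
| 7.1.4.1 table, <60 row | <60 | >60 |
| 7.1.4.1, first bullet | <60 | ≥75 |
| 7.1.4.1, glucagon and oral follow-on | at risk of severe hypoglycemia, no IV access | ≥75 |
| 7.1.4, 5-minute checks | monitoring | >75 |
| 5.14, discharge correction | <75 | ≥75 |
| 5.12.3.2 table, <60 row | challenge | >60 |
| 5.12.3.2, footnote | end of challenge | 75-120 |

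The two <60 rows can be read as first stages. In 5.12.3.2 the footnote supplies the next stage, and in 7.1.4.1 the first bullet supplies the final target. The 60-75 row of 7.1.4.1 has no such completion for a subject who was never below 60.

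**3. Two illustrative subjects outside the 5.12 table.**

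- *First seen at 65, still 65 at the check.* The 60-75 row gives the first dose of about 10 g. At the check, 65 > 60, so the printed rule calls for no repeat. The first bullet does not apply, because glucose was never below 60. The 5-minute checks continue, because 65 is not above 75, but 7.1.4 does not say what to give.
- *Raised from 55 to 65.* The stop in the <60 row is met (65 > 60), and so is the stop in the 60-75 row. The first bullet says to continue (65 < 75). Table and bullet disagree, and 7.1.4.1 states no hand-over between the rows.

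**4. After the change.** With ≥75 in the 60-75 row, check readings of 60 to 74 call for another dose of about 10 g, and 75 or above stops. The subject raised from 55 to 65 passes to the 60-75 row and is treated to ≥75, in agreement with the bullet.

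**The case against.** The strongest reply is that the table is indexed by current glucose. A check reading of 61-74 falls in the 60-75 row again, and that row directs a dose. With checks every 5 minutes until above 75, staff keep getting readings that lead back to it. This reading is available, and it is why the text cannot be said to rule out a second dose. But it reaches the right result only by ignoring the stop printed in the row.

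Second, subjects below 60 are already covered by the ≥75 bullet. That is correct, and it leaves mainly those first seen at 61-74.

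Third, the scope is narrow. During a challenge or monitoring period the 5.12 table governs, and it deliberately leaves 60-75 untreated under observation. This also stands. Lows outside the challenge table remain possible, for example in observation subjects under free-range control (4.4.14, 4.5.15, 4.6.14) or after the insulin that ends a hyperglycemia challenge (5.12.3.1). Because 7.1.4.1 does not define the monitoring period, how often its own table governs is unclear.

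Fourth, there are real safeguards. The row leaves treatment to what is appropriate and the investigator may treat on clinical grounds (7.1.4.1). Site safety guidelines apply and clinical staff are on the unit throughout (7.1.1), each site has safety plans (8.3), and glucose below 75 is corrected before discharge (5.14). These limit the harm. They do not make the row coherent.

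A reader might also infer that everything else in the protocol aims for 75. The documents do not support that. Both <60 rows print >60, and the 60-75 row of the challenge table gives no glucose. Section 5.14 releases a subject only at 100-300 and stable or rising, or above 75 to 100 and rising. After a hypoglycemic seizure or loss of consciousness, 7.1.4.1 sets 100-300.

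**Conclusion.** The point holds as a minor correction to safety text. The repeat rule in the 60-75 row defeats itself: its stop is 15 mg/dL below the ≥75 set for oral treatment of glucose below 60 in the same section, and the two stops disagree at 61-74 mg/dL. It matters only outside the 5.12 challenge table, and mainly for subjects first seen at 61-74.

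Two stronger conclusions are not supported. The text does not forbid a second dose, since a fresh look-up in the row or clinical judgment can supply one. And 87.5% is not a share of episodes or a measure of risk: it counts whole numbers in a range. The documents do not say how many episodes would be treated from this table, and none is estimated here.

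The conclusion assumes that the printed stop is meant to govern the repeat dose, and that the intended end point in this row is the ≥75 used in the bullets below it. No endpoint, sample size or analysis is affected.

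**What to change.** In the Protocol 7.1.4.1 table:

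- **60-75 mg/dL row:** change the stop from >60 to *until BG ≥75 mg/dL*.
- **<60 mg/dL row:** keep >60 and add *then continue per the 60-75 mg/dL row until BG ≥75 mg/dL*.

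Leave 5.12.3.2, the 5-minute monitoring rule in 7.1.4 and the 15-minute minimum between dose and check as they are. A subject raised from below 60 to 61-74 then has one dose (about 10 g) and one end point, in agreement with the first bullet.

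The cost is one threshold in one cell and one linking clause in the cell above it. Data collection and analysis do not change.

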7.1.5 Hyperglycemia and Blood Ketone Monitoring

The Subject will be asked to alert the study team anytime he or she notes symptoms of hyperglycemia (i.e. thirst, increased urination, or other symptoms). A glucose level will be confirmed by YSI or Subject SMBG meter.

If glucose >400 mg/dl and no symptoms and no ketones, the cause of the hyperglycemia will be investigated and treated as appropriate by the Investigator. Fingerstick blood ketones, using commercially available ketone meter will be monitored if blood glucose ≥ 300 mg/dl and hourly until resolved.

If blood ketones ≥ 0.6 mmol/L; subject participation in glucose challenges will be stopped for the day. Appropriate care will be provided, including fluids and insulin as determined by Investigator. Standard-of-care troubleshooting for insulin pump users will take place, including change of infusion set if indicated and insulin by injection if indicated.

During hyperglycemia challenge or monitoring period, site will follow section 5.12 hyperglycemia challenge table. Subject safety prevails and Investigator may treat for hyperglycemia when clinically indicated.

7.1.5.1 Treatment Guidelines for Hyperglycemia and Ketones

Subjects will be treated for hyperglycemia according to the following table:

Ketone				
		<0.6	0.6-1.5	>1.5
BG	<300		
 Glucose challenge will be stopped Ketone testing will be repeated hourly until <0.6 Subject will be treated with SQ insulin targeting 120mg/dL using subject's insulin sensitivity factor 	
 Accuracy (Sampling) visit will be stopped, only safety procedures will continue Ketone testing will be repeated hourly until <0.6 Subject will be treated with SQ insulin targeting 120mg/dL using subject's insulin sensitivity factor
	>300	
 Ketone testing will be repeated hourly until BG <300 	
 Glucose challenge will be stopped Ketone testing will be repeated hourly until <0.6 Subject will be treated with SQ insulin targeting 120mg/dL using subject's insulin sensitivity factor Continue monitoring until BG <300 	
 Accuracy (Sampling) visit will be stopped, only safety procedures will continue Ketone testing will be repeated hourly until <0.6 Subject will be treated with SQ insulin targeting 120mg/dL using subject's insulin sensitivity factor Continue monitoring until BG <300

- If the subject's glucose is >300 mg/dL or ketone level is ≥ 0.6 mmol/L on admission, the subject will be stabilized per the procedures above. The subject will continue to be monitored until a glucose level between 100-300 mg/dL and ketone measurement <0.6 mmol/L has been achieved (or the subject is discharged to an appropriate medical team). Blood sample collecting and analysis on YSI will continue during this time.
- Subsequently, glucose >300 mg/dL for >2 hours or glucose ≥ 400 mg/dL at any time will prompt discontinuation of the Hyperglycemia challenge.
- Ketones will be assessed hourly while the glucose is ≥ 300 mg/dL or the ketone level is ≥ 0.6 mmol/L.
- If the glucose is >300 mg/dL and ketone level is <0.6 mmol/L, corrective action will be taken only after it has been approximately 60-120 minutes from the last subcutaneous insulin dose. Specifically, the subject will be asked to bolus with his/her pump or deliver by injection an amount of corrective insulin that will bring him/her to a target glucose of 120 mg/dL.

- If the ketone level is ≥ 0.6 mmol/L, the cause of the elevated ketone level will be investigated (e.g. pump or pump site malfunction). Additional insulin may be administered either via insulin syringe or via a new pump site. The amount of insulin administered will be calculated using the subject's insulin sensitivity factor and a target glucose of 120 mg/dL.
- Insulin treatment for hyperglycemia or ketones should be done using the subject's own insulin. In the event that the subject's own insulin appears to be compromised (not having the expected effect on the subject's blood glucose), appropriate insulin (based on the subject's normal insulin type and concentration) provided by the site may be used.

If the ketone level is ≥ 1.5 mmol/L, the accuracy (sampling) visit will be stopped and the study MD or NP will take control of the subject's insulin dosing. The cause of the elevated ketone level will be investigated (e.g. pump or pump site malfunction). If the subject's home parameters are not felt to be working adequately due to hyperglycemia, ketonemia, or other factors (e.g. intercurrent illness), the study MD or NP will administer corrective insulin either via insulin syringe or via a new pump site using an ISF determined to be appropriate for the setting and a goal glucose of 120 mg/dL. The subject will continue to be monitored until a glucose level between 100-300 mg/dL and ketone measurement < 0.6 mmol/L has been achieved (or the subject is discharged to an appropriate medical team).

